4.1 Protocol Number

4.2 Investigator Identification

- Institution and affiliate name
- Investigator's name

4.3 Patient Identification

- Patient's initials (first and last)
- Patient's Hospital ID and/or Social Security number
- Patient demographics
 - Gender
 - Birth date (mm/yyyy)
 - Race
 - Ethnicity
 - Nine-digit ZIP code
 - Method of payment
 - Country of residence

4.4 Eligibility Verification

Patients must meet all of the eligibility requirements listed in Section 3.

4.5 Additional Requirements

Rev. Add2

4.5.1 Patients must provide a signed and dated, written informed consent form. This document may be signed patient's next of kin or person with power of attorney, if necessary.

NOTE: Copies of the consent are not collected by the ECOG-ACRIN Operations Office

Rev. Add2

NOTE: Patients should be consented only after APL diagnosis is confirmed.

Rev. Add2

4.5.1.1 Data collection for this study will be done exclusively through the Medidata Rave clinical data management system. Access to the trial in Rave is granted through the iMedidata application to all persons with the appropriate roles assigned in Regulatory Support System (RSS). To access Rave via iMedidata, the site user must have an active CTEP-IAM account (check at <https://ctepcore.nci.nih.gov/iam>) and the appropriate Rave role (Rave CRA, Read-Only, CRA, Lab Admin, SLA, or Site Investigator) on either the LPO or participating organization roster at the enrolling site. To hold Rave CRA role or CRA Lab Admin role, the user must hold a minimum of an AP registration type. To hold the Rave Site Investigator role, the individual must be registered as an NPIVR or IVR. Associates can hold read-only roles in Rave.

Upon initial site registration approval for the study in RSS, all persons with Rave roles assigned on the appropriate roster will be sent a study invitation e-mail from iMedidata. To accept the invitation, site users must log into the Select Login (<https://login.imedidata.com/selectlogin>) using their CTEP-IAM user name and password, and click on the "accept" link in the upper right-corner of the iMedidata page. Please note, site users will not be able to access the

study in Rave until all required Medidata and study specific trainings are completed. Trainings will be in the form of electronic learnings (eLearnings), and can be accessed by clicking on the link in the upper right pane of the iMedidata screen.

Users that have not previously activated their iMedidata/Rave account at the time of initial site registration approval for the study in RSS will also receive a separate invitation from iMedidata to activate their account. Account activation instructions are located on the CTSU website, Rave tab under the Rave resource materials (Medidata Account Activation and Study Invitation Acceptance). Additional information on iMedidata/Rave is available on the CTSU members' website under the Rave tab at www.ctsu.org/RAVE/ or by contacting the CTSU Help Desk at [name] or by e-mail at [contact].

5. Methodology Plan

There will be 7 investigators accruing at 6 different centers (LEAD SITES) who will serve as the APL experts for this proposal. The patients treated at these 6 centers will be enrolled at their particular institution. **The study will not be open at other academic centers.** The APL expert at each site will either manage the patient or provide consultative oversight to the treating team. The sub-investigators at lead sites can consent patients but it is expected that the local PI will provide oversight. We expect to enroll a maximum of 30% of the patients at these lead sites. Induction mortality is a problem in larger centers as well from extensive data that has been published. We postulate that using the guidelines along with expert input will improve outcome in lead sites. This will give us the opportunity to assess the problem as well as outcome in academic centers and compare the results to community centers. Since the accrual goal is 200 patients over a 4 year period, the accrual at lead centers will be limited to 60 patients over a 4-year period (30%). The Study Chair and ECOG-ACRIN office will monitor this closely and once the target is achieved, enrollment at lead sites will be put on hold. Investigators from the LEAD sites will meet or have a conference call twice a year to discuss the progress and results.

Prior to enrolling patients, while the study is being reviewed by the IRBs at the respective sites, the study investigators will contact NCORP community centers that are likely to treat APL in their catchment area. These visits will also be a part of publicizing the trial to ensure other treating physicians are aware of the study and also the risk of early deaths in this disease. In addition to physician visits, flyers and regular emails will also be sent out to ensure that there are frequent reminders about the study. At sites that open the trial there will also be a webinar to raise awareness for the trial and provide training on the treatment guidelines prior to study activation.

The trial will be conducted at NCORP community sites in addition to the Lead Sites. We conducted a survey of NCORP sites to assess their interest in participating in the study. The survey had 3 questions. a. Does your center treat patients with APL? b. Are you aware the induction mortality in APL is approximately 30%? c. Will your Center participate in a trial focused on decreasing induction mortality? Eleven sites responded and expressed interest. The PI and Co-PI will make personal contact with the other NCORP sites and present the goals of the trial and get other sites to open. We have also asked the NCORP leadership to give us an opportunity to participate in their annual meeting and conference calls and publicize the study to get more sites to participate.

5.1 Lead Sites

5.1.1 Lead Sites

- Medical College of Georgia at Augusta University.
- Memorial Sloan-Kettering Cancer Center, New York, NY
- The Mayo Clinic, Rochester, MN
- Northwestern University Feinberg School of Medicine, Chicago, IL
- Abramson Cancer Center of the University of Pennsylvania, Philadelphia, PA
- The Mayo Clinic, Jacksonville, FL

5.1.2 Patients treated at Lead Sites will be treated locally at the Lead Site using treatment guidelines. The local PI will provide expert support to

Rev. Add2

the treating team. The presentation of APL can be highly variable; hence adherence to the guidelines is not always feasible. Deviations that are made from the guidelines based on particular clinical situations will be documented in the medical record.

5.2 Outlying NCORP Community Facility

5.2.1 The study will be opened only at the NCORP community sites. **It will not be open at academic NCORP centers.** The treating physician from the NCORP community Facility should call the APL Expert in their catchment area for treatment guidance. Seeking advice from an APL expert is a key component of our model. The call should be made as soon as APL is suspected but no later than 3 days after starting ATRA and communication should be ongoing based on the clinical developments until a hematologic remission is achieved. The presentation in APL can be highly variable; hence complete adherence to the guidelines is not always feasible. Deviations that are made from the guidelines based on particular clinical situations will be documented in the medical record.

5.2.1.1 The provider at NCORP community centers will be the Hematologist/Oncologist attending caring for the patient. Initial contact has to be made by a Hematologist/Oncologist.

5.2.1.2 It is expected that the initial contacting Hematologist/Oncologist will continue the communication; alternatively, other members of the practice can communicate with the APL expert on an ongoing basis.

5.2.1.3 Trainees or advanced level practice providers (physician assistants or nurse practitioners) and trainees can be in communication subsequently with APL experts to continue the care.

5.2.2 A log will be maintained by the APL expert (Please see [Appendix II](#)). This will include information on Date admitted, date APL suspected, date APL confirmed, date APL therapy started and date APL expert was contacted. Subsequent calls and decisions made will be documented on the log sheet.

5.2.3 It will be suggested that the treating physician will also document the communication on an ongoing basis.

5.3 Study Accrual and Timeline

The study will accrue from years one to 4. Follow up will be for one year after last patient is accrued and accrual is completed. The total study duration is 5 years.

5.4 Adverse Event Reporting Requirements

The adverse events to treatment will be collected from the hospital records obtained from the patients induction period and also follow up at the treating physician's office. An AE log need not be maintained since this study will not include any new drugs. The complications from treatment will be noted in the database and will be used for analysis of outcomes. The only SAE that has to be reported is death.

5.4.1 Reporting Procedure

This study requires that expedited serious adverse event reporting use CTEP's Adverse Event Reporting System (CTEP-AERS). The CTEP's guidelines for CTEP-AERS can be found at <http://ctep.cancer.gov>. A CTEP-AERS report must be submitted electronically to ECOG-ACRIN and the appropriate regulatory agencies via the CTEP-AERS Web-based application located at <http://ctep.cancer.gov>.

In the rare event when Internet connectivity is disrupted a 24-hour notification is to be made by telephone to

- the SAE Team at ECOG-ACRIN [contact])
- the NCI [contact])

An electronic report MUST be submitted immediately upon re-establishment of internet connection.

Supporting and follow up data: Any supporting or follow up documentation must be uploaded to the Supplemental Data Folder in Medidata Rave within 48-72 hours. In addition, supporting or follow up documentation must be faxed to the NCI ([name]) in the same timeframe.

CTEP Technical Help Desk: For any technical questions or system problems regarding the use of the CTEP-AERS application, please contact the NCI Technical Help Desk at [contact] or by phone at [name].

Rev. Add2

5.4.2 Expedited Reporting Requirements for EA9131

Grade 5^a	
Unexpected	Expected
24-Hour 5 Calendar Days	24-Hour 5 Calendar Days
24-Hour; 5 Calendar Days – The AE must initially be reported via CTEP-AERS within 24 hours of learning of the AE, followed by a complete expedited report within 5 calendar days of the initial 24-hour report.	
^a This includes all deaths within one year of registration, regardless of cause. Thereafter, deaths must only be reported on the protocol specific case report forms.	
NOTE: A death due to progressive disease should be reported as a Grade 5 "Disease progression" under the System Organ Class (SOC) "General disorder and administration site conditions". Evidence that the death was a manifestation of underlying disease (e.g. radiological changes suggesting tumor growth or progression; clinical deterioration associated with a disease process) should be submitted.	

5.4.3 Other recipients of adverse event reports and supplemental data

ECOG-ACRIN will forward CTEP-AERS reports to the appropriate regulatory agencies and pharmaceutical company, if applicable.

Serious Adverse events determined to be reportable via CTEP-AERS must also be reported by the institution, according to the local policy

and procedures, to the Institutional Review Board responsible for oversight of the patient.

5.5 Completion of Induction

Induction will be continued until the patient achieves hematologic remission (as per guidelines).

5.6 Consolidation

Consolidation will be at the treating physician's discretion.

5.7 Maintenance

Maintenance will be per treating physician's discretion.

5.8 Duration of Follow-up

For this protocol, all patients, including those who discontinue treatment early, will be followed for survival for 1 year after the accrual is completed.

6. Study Parameters

NOTE: Please refer to Appendix I for all recommended tests and procedures

	Baseline
Confirmed APL Dianosis ¹	X
Referral to APL Expert ²	X
Informed Consent ³	X
Subject Registration ⁴	X

Rev. Add2

1. Positive t(15:17) by FISH OR conventional karyotype OR PML/RAR α by PCR, Rare variants can also be included if confirmed.
2. It is preferred that the APL expert for the catchment area is contacted, however, any APL Expert at any Lead Site may be contacted. Referrals must be made within 3 calendar days after ATRA or APL directed therapy is initiated.
3. Written informed consent must be obtained within 7 days of initiating APL directed therapy.
4. Registration can be done after initiating treatment.

Rev. Add2

7. Statistical Considerations

7.1 Study Design and Objectives

This study will accrue 200 APL patients over a 4-year period. The primary hypothesis is that the proposed process will lower the one-month mortality rate from 30% to < 15%. The primary endpoint is the one-month mortality rate. Secondary endpoints include: i) overall survival, one-year survival rate, ii) safety, iii) initiation of treatment from diagnosis, iv) survival in academic and community centers v) compliance with treatment guidelines and vi) evaluation of factors associated with outcome.

7.2 Sample Size Considerations and Monitoring Plan

Of the 200 patients accrued, it is expected to have 180 eligible patients after adjusting for ineligible and/or lost-to-follow up cases. We allowed 10% for ineligible and/or lost-to-follow-up cases. We often allow additional cases (up to 10%) to account for ineligible cases in ECOG studies. We do not expect any lost-to-fu cases at 1 month. However, we used 10% ineligibility and/or lost-to-follow-up to be conservative and general in this study.

After 100 patients (for 90 eligible) are enrolled and have followed for one-month mortality endpoint, one interim analysis will be conducted. Using the critical value corresponding to the O'Brien and Fleming boundary at 50% information time, 95% Repeated Confidence Interval (RCI) for the one-month mortality rate will be constructed. The result will be discussed with the ECOG-ACRIN DSMC members. If deemed efficacious, accrual will continue to 200 (for 180 eligible) patients. This design will have at least 90% power with a two-sided type I error rate of < 0.05. Another rationale for the sample size of 200 is that we would like to build a 95% RCI with a tight interval. For the expected one-month mortality rate, if the observed rate is 10% (18/180) the 95% RCI will be 6-15.4%. If the observed one-month mortality rate is 15%, the 95% RCI will be 10.1-21.1%.

We plan to limit the accrual from the large academic centers to a maximum of 30% of the total patients. Thus 60 patients (54 eligible) from major academic centers and 140 (126 eligible) from NCORP community sites are anticipated. The primary analysis and monitoring will be based on all patients regardless of enrollment site. After the study is completed, one-month mortality rate will be estimated for patients enrolled from NCORP and academic sites separately as a secondary analysis. With 126 eligible patients from NCORP sites, there will be at least 90% power for the hypothesis testing of reducing mortality rate from 30% to 15%, with a two-sided error rate of 0.05. There is sufficient power to test if one-month mortality rate for NCORP sites can be reduced from 30% to < 15%

For NCORP sites, 95% CI is 5.6-17% for the observed one-month mortality rate of 10.3% (13/126) and 95% CI is 9.3-22.5% for the observed one-month mortality rate of 15.1% (19/126). With 54 eligible patients from academic sites, there will be less than 80% power for the hypothesis testing of reducing mortality rate from 30% to 15%, with a two-sided error rate of 0.05. For academic sites, 95% CI is 3-20.3% for the observed one-month mortality rate of 9.3% (5/54) and 95% CI is 6.6-27.1% for the observed one-month mortality rate of 14.8% (8/54). Statistical analysis will be mostly descriptive for the secondary endpoints.

At 50% information time (i.e. 90 eligible patients have one-month mortality assessed), 95% Repeated Confidence Interval will be built for the one-month mortality estimate using the O'Brien-Fleming boundary for 50% information time. This analysis will be presented to the ECOG-ACRIN DSMC and discussed further.

We do not expect major safety issues in this study. However adverse events data will be monitored in ongoing basis and will be brought to ECOG-ACRIN DSMC attention.

7.3 Statistical Analysis Plan

7.3.1 Primary Objective

One-month mortality rate will be estimated by dividing total number of deaths within one month of study entry by total number of cases with at least one-month follow up data. 95% RCI will be provided for this endpoint. We will also evaluate the OS data using the Kaplan-Meier plot.

7.3.2 Secondary Objectives

Using the method of Kaplan-Meier, overall survival (OS) data will be described. The median OS and one-year OS rate will be estimated and 95% CI will be provided.

We confirm that the primary objective is to assess one-month mortality rate among all cases. Secondary analysis will involve evaluating outcome data in NCORP and academic sites separately. We clarified this further in Section [7.2](#). Overall the expected one-month mortality rate is in the range of 10-15% across all patients as well as in two subgroups of NCORP and academic sites.

With 200 (180 eligible) patients, we expect to build a confidence interval not wider than 11% for the expected one-month mortality rate of 10-15%. With 140 (126 eligible) cases from NCORP sites, the confidence interval for the one-month mortality rate will be not be wider than 13%.

For the safety endpoints, the severity and duration of coagulopathy, bleeding, infections and differentiation syndrome will be measured based on the CTC version 4.0. Analysis of the safety data will be mostly descriptive. The proportion of patients with the worst degree toxicity of grade 3 or higher will be assessed and presented with 95% CI. The length of hospital stay is defined as a period between the discharge and admission dates for the first hospitalization. For patients with no hospitalization, this will be defined as 0. To assess the associations between the length of hospital stay and toxicity measures (bleeding, infections, differentiation syndrome), each toxicity measures will be dichotomized as "mild" vs. "severe" and the length of hospital stay will be compared using the two-sample t-test.

The time from diagnosis and initiation of treatment will be assessed and dichotomized as "short" vs. "long" using the median value. One-month mortality rate will be compared in these two groups (short vs. long) using the Fisher's exact test. Overall-survival will also be

compared in these two groups using the logrank test. In this analysis, the time of diagnosis will be determined by both: i) confirmed diagnosis date and ii) date of suspicious APL. The dichotomized value of long vs. short based on the both times will be evaluated. Similarly the one-month morality rate and overall survival between the lead institutions and NCORP community centers will be compared. For all comparisons, two-sided p-values will be reported.

Compliance with treatment guidelines will be assessed as binary outcome and the successful compliance rate will be described with 95% confidence interval. A regression model will be developed to evaluate the factors associated with outcome. Data items such as age, risk status, comorbidity will be collected and evaluated.

Rev. Add2

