1.1 Rationale for Proposed Study

Acute Promyelocytic Leukemia (APL) is a highly curable malignancy with most large cooperative group trials showing a survival above 90%. Patients entered in cooperative group trials are a highly selected group of patients and may not be a representation of outcomes in the general population. It is also likely that patients may not even be seen at a large treatment center due to the advanced nature of the disease and/or socioeconomic and distance constraints. However in recent years, data from single institutions as well as large population data bases show that approximately 1 in 3 patients diagnosed with APL die within the first month of diagnosis.⁽¹⁻⁵⁾ The first group to systematically analyze this is a population-based study from Sweden. All patients diagnosed with APL between 1997 and 2006 in the Swedish Adult Leukemia Registry were included in the study. A total of 105 patients with APL were diagnosed during that time and thirty (29%) of these patients died within 30 days of diagnosis with 23 of these 30 patients dying within the first week of diagnosis. The major cause of death was reported as bleeding, with differentiation syndrome, sepsis and multi-organ failure being other causes contributing to early mortality.⁽¹⁾

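### Length of stay is compared by t-test between mild and severe toxicity with no allowance for in-hospital death, which can weaken the association or leave an undeclared survivors-only comparison

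*Combined protocol and SAP*

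**What the plan says.** Section 7.3.2 gives the definition: "The length of hospital stay is defined as a period between the discharge and admission dates for the first hospitalization". It adds one special case: "For patients with no hospitalization, this will be defined as 0". Bleeding, infections and differentiation syndrome are each split into mild and severe, with no cut-point stated for this split, and "the length of hospital stay will be compared using the two-sample t-test". The section also says that "For all comparisons, two-sided p-values will be reported", although "Analysis of the safety data will be mostly descriptive".

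No section says how a stay that ends in death is recorded or analysed.

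The same section expects one-month mortality of 10-15%. Section 1.1 reports a Swedish registry in which 30 of 105 patients died within 30 days, "with 23 of these 30 patients dying within the first week of diagnosis". Bleeding was the main cause there, and differentiation syndrome and sepsis contributed. Section 1.2 gives a similar list of causes for Brazil.

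**The concern.** A two-sample t-test on days in hospital treats a short stay as one kind of outcome. In this disease a stay can be short because the patient recovered quickly or because the patient died early. The toxicities that define the severe groups are among those the protocol names as causes of early death, so early ending of the stay is tied to the grouping variable.

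The text leaves two readings open. If the date of death is entered as discharge, fatal cases pull the severe-group mean down, and a real link between severe toxicity and longer stay can be missed. If a patient who dies has no discharge date and drops out, the comparison is restricted to survivors without being labelled so, and it loses the most severe cases. With no rule, the choice can be made after the data are seen.

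**Working it through.** The documents give no expected stay, SD, power or group size for this comparison, so there is no planned figure to reproduce.

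**Inputs from the documents**
- Eligible patients: 180 (Section 7.2).
- Expected one-month mortality: 10-15% (Section 7.3.2), so 0.10 × 180 = 18 to 0.15 × 180 = 27 deaths.
- Share of early deaths with hemorrhage: 41% to 66% where reported (Section 1.1, Figure 1), and 48% in the programme in Brazil, Mexico, Chile and Uruguay (Section 1.2).

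**Assumptions not in the documents**
- Mean stay of survivors: 35 days (severe), 28 days (mild). Mean stay of patients who die: 8 days.
- 45 severe and 135 mild patients for bleeding.
- All one-month deaths occur during the first stay. Deaths with hemorrhage fall in the severe bleeding group and the rest in the mild group.

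**Reading 1: death date taken as discharge**

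With d deaths and a share s of them in the severe group:

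difference (severe minus mild) = (35 − 28) − (35 − 8) × d × s/45 + (28 − 8) × d × (1 − s)/135

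- d = 18: 7 − 10.8s + 2.67(1 − s) = 9.67 − 13.47s
- d = 27: 7 − 16.2s + 4(1 − s) = 11 − 20.2s

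| Share s of deaths in severe group | 18 deaths | 27 deaths |
|---|---|---|
| 41% | +4.1 days | +2.7 days |
| 48% | +3.2 days | +1.3 days |
| 54% | +2.4 days | +0.1 days |
| 66% | +0.8 days | −2.3 days |

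The difference among survivors is +7 days in every cell. The sign changes at s = 9.67/13.47 = 72% with 18 deaths, which is outside the reported shares, and at s = 11/20.2 = 54% with 27 deaths.

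**Sensitivity to the assumptions**

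Take a true difference of +5 days (33 against 28), with deaths again at day 8.
- 60 severe, 120 mild: 8 − 10.5s with 18 deaths, giving +3.7 to +1.1 days over s = 41-66%; 9.5 − 15.75s with 27 deaths, giving +3.0 to −0.9 days.
- 90 severe, 90 mild: 9 − 9s with 18 deaths, giving +5.3 to +3.1 days; 11 − 13.5s with 27 deaths, giving +5.5 to +2.1 days.

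The distortion therefore depends on how large the severe group is. It is greatest when that group is small. With equal groups and the lowest share it disappears or turns slightly the other way.

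**Limiting case: every death in the severe group**

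The sign changes when the fraction dying in that group reaches (35 − 28)/(35 − 8) = 26%. Over mild stays of 25-30 days, an excess of 3-7 days in severe survivors and death at day 5-14, the threshold runs from 3/(3 + 30 − 5) = 11% to 7/(7 + 25 − 14) = 39%.

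**Reading 2: deaths dropped**

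Under the main assumptions the difference stays at +7 days, but it describes survivors only. With 18 deaths and s = 66%, about 0.66 × 18 = 12 of 45 severe patients (26%) leave the comparison, against about 6 of 135 mild patients (5%).

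**The case against.** A reader might infer that the plan counts early deaths as short stays. The documents do not say so. They are silent, and Section 8 refers to separate Forms Completion Guidelines whose coding of discharge and death cannot be seen here. That objection stands, so the point is a missing rule together with a test that cannot accommodate death.

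A reader might also infer that nearly all deaths fall in the severe group, and that severe toxicity would routinely appear to shorten the stay. The documents do not support this either. Each toxicity is tested separately, and hemorrhage is reported in 41-66% of early deaths, so the remaining 34-59% could sit in the mild bleeding group. A 40% death rate among 45 severe patients would need all 18 deaths expected at 10% mortality to fall in one toxicity's severe group.

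The first-week deaths in the Swedish registry do not carry over directly. Under Sections 3.1.3 and 4.5.1, consent follows a confirmed diagnosis and may come as late as day 7 of therapy, so some of the earliest deaths will never be enrolled.

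Finally, length of stay is not named in the objectives (Section 2) or the endpoint list (Section 7.1). This supports a low severity. It does not remove the point, because a specific test and two-sided p-values are planned.

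**Conclusion.** The point holds as a minor one. The planned t-test makes no allowance for in-hospital death in a setting where 18 to 27 early deaths are expected, partly from the toxicities that define the groups. One reading of the plan gives a comparison distorted by death, and the other an unlabelled survivors-only comparison.

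Under the main assumptions, taking death as discharge cuts a true +7 days to between +4.1 and +0.8 days with 18 deaths, and to between +2.7 and −2.3 days with 27. Substantial weakening is the usual result when the severe group is a minority. Reversal is confined to the upper end of both mortality and hemorrhage share.

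These sizes rest on assumed stays and group sizes and on a split of deaths that the documents support only for bleeding; no comparable share is given for infection or differentiation syndrome. The analysis is secondary and mostly descriptive, and the one-month mortality endpoint is unaffected.

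**What to change.** Replace the t-test in Section 7.3.2 with one of these, chosen in advance:

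- Time from admission to discharge alive, with in-hospital death as a competing event: cumulative incidence by toxicity group, compared by Gray's test.
- A Wilcoxon test on length of stay with in-hospital deaths ranked as the worst outcome.

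Report stay among patients discharged alive as description only, with the number of in-hospital deaths in each group beside it. State the cut-point between mild and severe, and say how patients who were never hospitalised enter the chosen analysis.

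The cost is SAP wording, slightly more analysis work and a summary less simple than a difference in means. No new data are needed: the stay definition already requires admission and discharge dates, and deaths are captured for the primary endpoint and under Section 5.4.2. Stating the handling of deaths in one sentence would remove the ambiguity, but keeping the t-test would still leave one of the two weak comparisons.
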